Caffeinated chewing gum improves sympathetic nerve activity and simulates wrestling performance: a double-blind crossover trial

Document Date: Dec 25, 2024

IRB approved date: March 3, 2024

Project summary

The purpose of this study was to investigated whether caffeine intake is effective in improving the performance of wrestlers in a simulated competition. The study was designed to involve 16 healthy adult male athletes who had been trained in professional wrestling and were divided into caffeine trial (CAF trial) and placebo trial (PL trial) in a randomized crossover double-blind study design. After three days of dietary control, participants arrived at the laboratory in the afternoon of the day of the trial to collect saliva samples in a quiet state and were fitted with a heart rate monitor. Participants chewed either caffeine-containing gum at 3 mg/kg body weight (CAF trial) or placebo-containing gum without caffeine (PL trial) for 10 minutes and then spit it out. Participants then underwent a 15-minute dynamic warm-up. At the end of the warm-up, participants performed 2 rounds of 3-minute wrestling-specific simulated matches, and the number of falls in the simulated matches was recorded. After the simulation match, saliva samples were collected from the participants again. The saliva samples were analyzed for caffeine alpha-amylase concentration. Differences between the two trials were analyzed using a paired sample t-test and significance was set at $\alpha < 0.05$.

Introduction

At the Olympic Games and the World Athletics Championships, wrestling is one of the most popular event. In addition to specialized skills, the key to winning a wrestling match is muscle strength and anaerobic power (1, 2). In a previous study, 92 male wrestlers were divided into elite and non-elite groups according to their performance, and it was found that absolute muscular strength and anaerobic power were the key factors that differentiated elite wrestlers from non-elite wrestlers(2). From these studies, it appears that improving strength as well as anaerobic power of a wrestler is an important factor in winning a competition.

Many studies have suggested that caffeine (1,3,7-trimethylxanthine) supplementation prior to exercise is effective in improving maximal muscle strength and anaerobic capacity, with approximately small to moderate improvements (3). It has been established that the mechanisms in question consist of antagonised adenosine receptors.

The resulting effect of this is a reduction in the level of fatigue experienced during periods of physical exertion. Furthermore, it has been demonstrated that the release of calcium ions from the sarcoplasmic reticulum is increased, while at the same time the activity of sodium-potassium ATPase (Na^+/K^+ -ATPase) is maintained. In addition to the abovementioned effects, it has been observed that the aforementioned mechanisms stimulate glycolysis (4, 5). A dose of 3-6 milligrams of caffeine per kilogram of body weight is recommended before exercise. This can be achieved through energy drinks or capsules(3).

Another physiological mechanism that may affect maximal muscle strength and anaerobic power may be related to the activation of sympathetic nerves. Recent studies have demonstrated that enhanced sympathetic activation during exercise can be an effective strategy for reducing fatigue and increasing energy output at maximum intensity (6, 7). In order to comprehend the status of sympathetic nerve activation, it is possible to quantify the electrocardiographic signal from the heart, the α -amylase levels in saliva, or the plasma catecholamine concentration (8). Caffeine supplementation has been demonstrated in previous studies to enhance sympathetic nerve activity(9). In addition to the ingestion of capsules, the chewing of caffeinated gum has been observed to enhance sympathetic nerve activity and significantly reduce fatigue during maximal sprinting(7).

It has been demonstrated that chewing caffeinated gum can enhance the rate of caffeine absorption, leading to a more expeditious attainment of the maximum blood concentration of caffeine(10). The absorption of caffeine from chewing caffeine gum is a process that occurs through the mucous membrane of the oral cavity. The rate of absorption is such that the highest concentrations of caffeine in the blood can be reached within approximately fifteen minutes after chewing (11). With regard to the effects of caffeine on exercise performance, studies based on systematic reviews and meta-analyses have found that the ingestion of caffeine chewing gum at a dose greater than 3 mg/kg of body weight prior to exercise can effectively improve maximal muscular strength and anaerobic power (12). In the case of weight classes being required for events such as wrestling, the caffeinated chewing gum has been demonstrated to reduce water intake and may decrease the risk of being overweight. This may serve as an additional effective method of supplementing caffeine intake. The purpose of this study was to investigate the effect of caffeinated chewing gum on sympathetic nerve activity on wrestling simulation match.

Methods

Study design

In this study, a double-blind crossover experimental design was used, in which participants were randomised to either the caffeinated chewing gum trial (CAF) or the placebo chewing gum trial (PL). After a seven-day washout period, the participants were switched to another trial of experiments (Figure 1). All tests were conducted after a regular 6-day training period with a day off to ensure that participants were in a similar physiological state prior to the experiment. Prior to the experiment, participants were asked to perform at least 2 simulated matches to familiarise with the simulated matches before the main experiment. The primary outcome measure was the number of falls in the simulated match, while the secondary outcome was α -amylase concentration in saliva, as an indicators of sympathetic nerve activity. The study commenced on 11 June 2024 and concluded on 23 December 2024.

Participants

Seventeen professionally wrestling male athletes were recruited for this study. After one participants withdrew due to personal reasons, the final results of 16 participants (age: 21.8 ± 1.0 years; height: 168.4 ± 4.5 cm; mass: 68.2 ± 8.7 kg) were analyzed. The inclusion criteria for this study were: (i) more than 6years of professional wrestling training; (ii) more than 6 months of continuous training; (iii) recovering from sports injuries such as strains and contusions for at least 3 months. The exclusion criteria were: (i) non-professionally wrestling athlete; (ii) none regular training in the past 6 months; (iii) less than 3 months of recovery from a sports injury, or present epilepsy, hypertension, hyperlipidemia, heart disease, arthritis, osteoporosis, or brain injury; (iv) a history of caffeine allergy. The consent form is completed after the participant has given consent. This study was conducted following the Declaration of Helsinki.

Sample size calculation

In this study, the number of participants in request was analysed using the G*Power software (version 3.1.9.4, Universität Düsseldorf, Germany) (13). In a previous study, 12 wrestling athletes were given the Pittsburgh Wrestling Performance Test (PWPT) after a caffeine intake and found that supplementation with a high dose of caffeine significantly reduced the completion time (56.8 ± 2.0 vs. 52.9 ± 1.8 s; $p < .05$) of the PWPT. Based on this data, we calculated that the effect size of this study reaches 2. The calculation was based on an alpha level of 0.05 and a correlation coefficient of 0.80, it was calculated that 6 participants would be sufficient to meet the requirement of participants.

Protocol

Prior to the first official test, the participant must record the diet and training for the 3 days prior to the test, and consume the same diet and training before the next test. On the day of the test, the same breakfast and lunch will be provided to the participant to ensure the same energy intake before the test.

All the experiments were conducted at 3pm. Upon arrival at the laboratory, the participants were required to undergo saliva collection. Three milliliters of saliva were spat into a saliva tube for later analysis. After the participants putted on heart rate monitor, participants were instructed to chew either caffeine-containing gum (3 mg/kg body weight) or a caffeine-free placebo gum for a period of 10 minutes. Thereafter, the gum was to be expectorated. Following this, the participants underwent a dynamic warm-up for a period of 15 minutes. It has been established that the highest blood concentration of caffeine is achieved 15 minutes after the chewing of the gum and subsequent expulsion(11). After warming up, participants are permitted to engage in any form of self-stimulation they deem appropriate, including yelling, punching the dummy, and other similar actions. The present action has been meticulously designed to enhance sympathetic nerve activity. This finding serves to corroborate the hypothesis that caffeine supplementation exerts a stimulant effect on sympathetic nerve activity.

After warming up, the grip strength of the participant's hands was measured with a grip strength meter (Smedley's Hand Grip Dynamometer TTM, Tokyo, Japan). Subsequently, participants engaged in a 3-minute, 2-round simulated wrestling match. This simulation has been shown to have good reliability and validity(14). In each 3-minute round of the simulation, one dummy fall was performed in the first 30 seconds, with an interval of 10 seconds each time. The participants then try to complete the maximum number of falls in 20 seconds. After the fall, the participants were given a 10-second break for a total of 1 minute. The same pattern was followed in the 2nd and 3rd minutes. During the 3rd minute, the duration of continuous wrestling was extended to 30 seconds. After a 30-second break, the participant repeated the same simulation and record the total number of falls. After the simulation competition, saliva was collected again and caffeine concentration and α -amylase concentration were measured.

Caffeine and placebo gum

The caffeinated chewing gum employed in the present study (Military Energy Gum, Arctic Mint flavour; Stay Alert, Chicago, USA) has been utilised in previous studies(7, 10). It is estimated that a single piece of gum contains approximately 5 grams and 100 milligrams of caffeine. The placebo gum was a commercially available blue mint gum

(Lotte Gum Mint., Ltd., Tokyo, Japan). In order to administer a dose of 3 mg/kg of caffeine per unit of body weight, it was necessary to crush, grind, blend, reshape and flavor all chewing gums with 0.3 g of peppermint-flavored powder. The process was designed to ensure that the new chewing gums were comparable to the original in terms of appearance, color, flavor, weight and size. Previous studies have demonstrated that this method renders it impossible for the participant to distinguish the type of gum (7, 15).

Saliva sample collection and analysis

Saliva samples were stored in a refrigerator at -80 degrees immediately after collection. For analysis, samples were thawed and centrifuged at 4000 rpm for 5 min. 500 μ L of saliva samples were transferred to glass tubes for mass spectrometry analysis and Enzyme-linked immunosorbent assay (ELISA) analysis respectively. The analysis of saliva α -amylase concentration was conducted utilising an enzyme-linked immunosorbent assay (ELISA) with commercially available reagents (Neogen Corporation, Kentucky, USA; Salimetrics LLC, State College, PA, USA).

Statistical analysis

All data are presented as means \pm standard deviations. The Shapiro–Wilk test was utilised to evaluate the normality of the data. The grip strength and number of fall on each rounds between the two trials were analyzed using paired t-tests. The saliva caffeine and α -amylase concentration and RPE were analyzed using two-way ANOVA with repeated measures. If the interaction effect (trial \times time) were significant, the Bonferroni method was used to perform post hoc comparisons. Effect sizes were calculated using Cohen's d to quantify the magnitude of observed effects and defined as trivial (<0.20), small (0.20 – 0.40), moderate (0.40 – 0.80), and large (>0.8), respectively. The power value of each data was conducted using G*Power 3.1.9.6 software (13).

Reference

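### The two-period crossover is analysed without a period term: a shift between visits costs precision, and biases the caffeine estimate if the two orders are also unequal

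*Protocol*

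**What the plan says.** The Study design section describes a randomised, double-blind, two-period crossover of caffeinated gum (CAF) and placebo gum (PL): "After a seven-day washout period, the participants were switched to another trial of experiments". The primary outcome is the number of falls in the simulated match. Seventeen athletes were recruited and 16 analysed (Participants). The numbers allocated to, or analysed in, each order are not stated.

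The analysis is fixed in two places:

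- Project summary: "Differences between the two trials were analyzed using a paired sample t-test".
- Statistical analysis, for grip strength and falls: "number of fall on each rounds between the two trials were analyzed using paired t-tests". For the saliva measures and perceived exertion: "RPE were analyzed using two-way ANOVA with repeated measures", with trial and time as the factors.

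For saliva, time means the sample before the gum versus the sample after the match, both within one visit. It does not distinguish the first visit from the second.

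The protocol does act to keep the two visits alike: "participants were asked to perform at least 2 simulated matches to familiarise with the simulated matches before the main experiment"; "All tests were conducted after a regular 6-day training period with a day off"; participants repeat their recorded habits ("consume the same diet and training before the next test"); breakfast and lunch are provided and identical; and "All the experiments were conducted at 3pm".

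**The concern.** In a two-period crossover, visit 2 can differ from visit 1 for reasons unrelated to the gum, such as residual learning, familiarity with the full test day, or changes in condition or motivation. The protocol's controls make this less likely but do not exclude it. The concern is only with what remains after them.

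A remaining shift favours caffeine in participants who take it second and counts against it in those who take it first. A plain paired t-test cannot separate this from random variation. With equal orders the shift cancels from the mean difference but stays in its SD. With unequal orders part of it is also credited to, or taken from, caffeine. A period term removes the shift from both the mean and the SD, using data the study already has.

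**Working it through.** **Inputs.** From the protocol: N = 16 analysed, 17 recruited, planning effect 2, alpha 0.05, correlation 0.80. Assumed, because the protocol does not give them: a two-sided test, the order split (8:8 to 11:5), and the shift, written k = (visit 2 minus visit 1) / SD of the paired difference within an order, taken from 0 to 1.

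**The plan's own figure.** With a standardised paired effect (dz) of 2 and two-sided 5%, n = 6 gives 97.1% power and is the smallest n that reaches 95%. The stated 6 is therefore reproducible and does not depend on the period term.

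**Model.** Let y = CAF minus PL. For PL first, y = effect + shift + error. For CAF first, y = effect − shift + error.

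**Bias of the paired mean** = shift × (number PL first − number CAF first)/16. For an excess of PL first this is 0 at 8:8, 2/16 = 0.125 × shift at 9:7, 4/16 = 0.25 × shift at 10:6 and 6/16 = 0.375 × shift at 11:5. The sign reverses if CAF first is the larger group. If 17 were allocated 9:8 (an assumption), one loss leaves 8:8 or 9:7.

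**Interval width at 8:8**, in within-order SD units:

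- Paired: t(15 df) × √(1 + 16k²/15)/4, with t = 2.131. This gives 0.533, 0.550, 0.600 and 0.766 for k = 0, 0.25, 0.5 and 1.
- Period-adjusted: t(14 df) × ½√(1/8 + 1/8) = 2.145 × 0.25 = 0.536 for every k.
- Ratio paired/adjusted: 0.99, 1.03, 1.12, 1.43.

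**Break-even shift.** For orders of size n1 and n2, solve t15²[1 + k²(4·n1·n2/16)/15]/16 = t14²(1/n1 + 1/n2)/4. The adjusted interval is the narrower once k exceeds 0.11 (8:8), 0.17 (9:7), 0.28 (10:6) or 0.44 (11:5).

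**Power at 8:8** (simulation for the paired t). With r = 0.80 and equal SDs, dz = d/√(2 × 0.20) = d/√0.4.

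| d (dz) | Paired, k = 0 | 0.25 | 0.5 | 1 | Adjusted, any k |
|---|---|---|---|---|---|
| 0.4 (0.63) | 66% | 63% | 56% | 33% | 65% |
| 0.47 (0.75) | 80% | 78% | 72% | 49% | 80% |
| 0.6 (0.95) | 94% | 93% | 91% | 76% | 94% |
| 0.8 (1.26) | 99.7% | 99.6% | 99.3% | 97% | 99.7% |

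At dz = 2 power stays at about 100% even at k = 1. At d = 0.2 it is about 22% with or without the period term when there is no shift.

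**Type I error of the paired t** (nominal 5%):

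| Split | k = 0.5 | k = 1 |
|---|---|---|
| 8:8 | 2.9% | 0.6% |
| 9:7 | 3.4% | 1.2% |
| 10:6 | 4.9% | 3.7% |
| 11:5 | 7.5% | 10.0% |

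The adjusted test holds 5% at each of these splits. Under simple randomisation (an assumption), an exact 8:8 has probability 19.6% and 11:5 or worse 21%. Weighting the splits by Binomial(16, 0.5), the paired t-test's error averages 5.0%, 5.0% and 5.1% for k = 0.25, 0.5 and 1.

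**Cost if there is no shift.** At dz = 0.75 the paired t has 80.1% power. The adjusted test (noncentral t, 14 df, noncentrality 0.75 ÷ ½√(1/n1 + 1/n2)) has 79.7% at 8:8, 79.0% at 9:7, 77.1% at 10:6 and 73.5% at 11:5.

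**The case against.** The strongest reply is that the paired t-test is valid here. Over a symmetric randomisation its bias is zero and its type I error is about 5%, so what is at issue is efficiency, plus bias under an unlucky split. That is correct, and no general false-positive inflation is claimed.

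Both driving quantities are assumed, and the protocol's controls argue for a small shift. The largest losses need k = 1, a shift as large as the whole within-order SD. At k = 0.25 and 8:8 the loss against adjustment is about 2 power points or less, and at the planning effect of 2 there is none. This also stands and limits the weight of the point. The smaller effects in the power table are illustrative: the Introduction's small-to-moderate gains describe caffeine literature on strength and anaerobic capacity, not falls, and r = 0.80 comes from a sample size calculation based on a completion-time outcome.

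Adjustment is not free. Below the break-even shifts it widens the interval, and at 11:5 with no shift it costs 80.1 − 73.5 = 6.6 power points. But that is also the split where an unadjusted shift does most harm, and at 8:8 or 9:7 the cost is 1 point or less.

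Finally, the protocol is dated 25 December 2024, two days after the study closed, so a new primary analysis could look post hoc. That affects how the change is declared, not whether period belongs in the model.

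**Conclusion.** The concern holds. Every analysis the protocol names for this randomised two-period crossover lacks a period term, and these are stated choices, not details left open. The consequence is conditional. If a visit shift remains, the paired analysis loses precision (3% to 43% wider intervals for k from 0.25 to 1 at 8:8). If the orders are also unequal, it is biased by the imbalance fraction times the shift, in either direction. Nothing in the protocol shows that such a shift or imbalance occurred. The figures assume an additive shift, normal errors and complete data on 16 participants; unequal carryover is a different matter. The loss bears on the conclusion only if the true effect is well below the planning value of 2. The change is worth making because it is cheap, but the omission does not invalidate the trial.

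**What to change.** Analyse total falls (the primary outcome in Study design) and grip strength with treatment and period as fixed effects and participant as a random effect. With complete data this equals half the difference between the two order groups in their mean within-participant period difference, on 14 degrees of freedom. A sequence term is optional, since it does not then change the treatment estimate.

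Add period to the saliva and perceived-exertion models. Include period × time where the trial × time interaction is tested, because a visit shift common to both samples cancels from that interaction but a shift in the within-visit change does not.

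Report the number of participants per order, as randomised and as analysed. If results have already been seen, date the change and show the paired t-test beside the adjusted result.

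The cost is a line or two of analysis wording, one degree of freedom (15 to 14) and no new data, plus the small power loss given above if there is no shift.

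### The requirement of 6 participants belongs to completion time in another wrestling test, not to falls; say so, state what 16 can detect for falls, and report confidence intervals instead of a power value

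*Protocol*

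**What the plan says.** The Sample size calculation section of the Protocol cites a previous study of 12 wrestlers in which "supplementation with a high dose of caffeine significantly reduced the completion time" of the PWPT, from 56.8 (SD 2.0) to 52.9 (SD 1.8) s. It continues: "we calculated that the effect size of this study reaches 2". The remaining inputs are given as "The calculation was based on an alpha level of 0.05 and a correlation coefficient of 0.80", and the conclusion is that "it was calculated that 6 participants would be sufficient to meet the requirement of participants". Target power and sidedness are not stated.

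Under Study design, "The primary outcome measure was the number of falls in the simulated match". The section headed Protocol describes that match as two 3-minute rounds of dummy falls after gum at 3 mg/kg: "After a 30-second break, the participant repeated the same simulation and record the total number of falls". Results from 16 participants were analysed.

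The Introduction describes caffeine before exercise as "effective in improving maximal muscle strength and anaerobic capacity, with approximately small to moderate improvements". The Statistical analysis section plans paired t-tests of falls in each round and uses Cohen's d "to quantify the magnitude of observed effects and defined as trivial (<0.20), small (0.20 – 0.40), moderate (0.40 – 0.80), and large (>0.8"). Its next and last sentence has a power value computed in G*Power for every outcome.

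**The concern.** The calculation concerns a time in seconds on one test after a high dose. The trial's primary outcome is a count on another test after 3 mg/kg gum. Borrowing from a neighbouring study is ordinary practice, but the Protocol calls the borrowed value the effect of this study and gives no argument that it carries over. It also gives no expected difference or SD for falls.

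What is at stake is how the primary result is read. Someone who sees 16 analysed against 6 required may assume a wide margin for falls and take a non-significant result as strong evidence of no effect. The G*Power sentence invites a related mistake. If the power is computed from the observed effects, it carries no information beyond the p-value.

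**Working it through.** **Inputs from the Protocol.** PWPT times 56.8 (SD 2.0) and 52.9 (SD 1.8) s; alpha 0.05; correlation r = 0.80; stated requirement 6; 16 analysed; paired t-tests; the 'moderate' band for d, 0.40 to 0.80.

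**Assumptions.** Two-sided test. The correlation between a participant's falls in the two trials is not given, so r = 0.5, 0.8 and 0.9 are used. The SD of falls is not given, so results are in SD units.

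**Formulas.** dz = mean difference / SD of differences, which for equal SDs is d / √(2(1 − r)). Power is the probability that a noncentral t with n − 1 degrees of freedom and noncentrality dz√n falls beyond the two-sided critical value.

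**1. The stated 6.** d = 3.9 / √((2.0² + 1.8²)/2) = 3.9/1.90 = 2.05, taken as 2. With 2 entered directly as dz, power is 0.909 at n = 5 and 0.971 at n = 6. A 95% target therefore gives 6; 80% or 90% gives 5.

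**2. With the stated r = 0.80.** SD of differences = √(2.0² + 1.8² − 2 × 0.80 × 2.0 × 1.8) = √1.48 = 1.217 s, so dz = 3.9/1.217 = 3.21. Power is 0.789 at n = 3, 0.981 at n = 4 and 0.999 at n = 5. The requirement is 4 for targets of 80% to 95%, and 5 for 99%. So r = 0.80 does not appear to have entered the printed figure, and leaving it out made the figure larger.

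**3. What 6 and 16 give for falls** (one paired t-test, two-sided alpha 0.05).

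| n | r | power at d = 0.4 | power at d = 0.8 | d detectable at 80% power |
|---|---|---|---|---|
| 6 | 0.5 | 13% | 36% | 1.43 |
| 6 | 0.8 | 24% | 70% | 0.91 |
| 6 | 0.9 | 43% | 93% | 0.64 |
| 16 | 0.5 | 32% | 85% | 0.75 |
| 16 | 0.8 | 66% | 99.7% | 0.47 |
| 16 | 0.9 | 92% | over 99.9% | 0.34 |

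The detectable dz is 1.43 with 6 participants and 0.75 with 16. If alpha is split over the two rounds (0.025 each), 16 participants detect dz = 0.84, that is d = 0.84, 0.53 or 0.38 at r = 0.5, 0.8 or 0.9.

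**4. Observed power.** Setting the noncentrality equal to the observed t with n = 16, p = 0.05 (t = 2.13) gives 51% and p = 0.20 (t = 1.34) gives 24%. Each p-value maps to one power value.

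**5. What a confidence interval gives.** The 95% half-width at n = 16 is 2.131/√16 = 0.533 SDs of the paired difference. In SDs of a single trial this is 0.533 × √(2(1 − r)), or 0.53 at r = 0.5 and 0.34 at r = 0.80.

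**The case against.** The Protocol already names the PWPT, the outcome, the population and the means and SDs, so the origin of 2 is visible, and it never claims a margin of 16 over 6 for falls. The study ended on 23 December 2024, so no sizing decision is open. This stands, and it makes the point minor. What remains is that the value is attributed to this study and the resulting 6 is presented as its requirement.

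Four stronger conclusions might be inferred, and the document does not support them.

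- *The trial is too small.* Nothing shows this. At r = 0.9, 16 participants have 92% power even at d = 0.4; at r = 0.5 they have 32%. The correlation for falls is unknown.
- *The arithmetic understates the need.* It does not. The stated r = 0.80 would give fewer than 6.
- *An effect of 2 is refuted by the Introduction.* The Introduction speaks of strength and anaerobic capacity in general, on an unstated scale. The bands in the Statistical analysis section are for describing observed results. That 2 is 2.5 times 0.80 leaves it unsupported for falls, not disproved.
- *The G*Power value is certainly observed power.* The Protocol does not say so. This is an inference from its place directly after the observed effect sizes and from its covering every outcome.

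Confidence intervals could also be specified in an analysis plan that is not at hand. The objection here is to the power sentence that the Protocol does contain; intervals are the better replacement for it.

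**Conclusion.** The point holds as a minor reporting and interpretation correction. The figure 6 is a calculation for PWPT completion time. It cannot be read as the requirement for falls, because across d = 0.4 to 0.8 it gives anything from 13% to 93% power over r = 0.5 to 0.9 (24% to 70% at r = 0.80). The 16 analysed detect dz = 0.75 at 80% power for a single test of falls, or 0.84 if alpha is split over the rounds.

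These figures rest on a two-sided paired t-test and an assumed correlation, and cannot be turned into a number of falls without an SD. A null result on falls should be read from the paired difference and its interval, not from a surplus over 6 or from a power value.

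**What to change.** **Sample size calculation.** Attribute the effect size of 2 to PWPT completion time in the previous study instead of to this study. State the target power and sidedness used. Then add:

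*For falls, 16 participants give 80% power (paired t-test, two-sided alpha 0.05 per test) for dz = 0.75, that is d = 0.75, 0.47 or 0.34 for an assumed within-participant correlation of 0.5, 0.8 or 0.9. If alpha is split over the two rounds (0.025 each), dz = 0.84, that is d = 0.84, 0.53 or 0.38.*

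**Statistical analysis.** Replace the closing sentence on the G*Power power value with:

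*The mean paired difference (CAF minus PL) and its 95% CI are reported for falls (each round and total), grip strength, and the change in salivary alpha-amylase.*

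This includes the secondary outcome, which the present power sentence also covers.

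**Cost.** Wording in two places and one interval per comparison, with no extra participants and no change of test. The downside is that the stated figure for falls looks less favourable than the apparent surplus of 16 over 6.

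### The only post-gum alpha-amylase sample follows the match, so it can show a total effect of the gum but not one independent of work done or one that explains the falls

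*Protocol*

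**What the plan says.** The Introduction ends: "The purpose of this study was to investigate the effect of caffeinated chewing gum on sympathetic nerve activity on wrestling simulation match". Earlier it presents sympathetic activation as a possible mechanism behind strength and anaerobic power, citing evidence that "enhanced sympathetic activation during exercise can be an effective strategy for reducing fatigue and increasing energy output at maximum intensity". Under Study design, falls in the simulated match are the primary outcome, and salivary alpha-amylase is the secondary outcome, as the indicator of sympathetic nerve activity.

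The Methods subsection headed Protocol fixes two saliva samples. The first is before the gum: "Upon arrival at the laboratory, the participants were required to undergo saliva collection". The second is after the match: "After the simulation competition, saliva was collected again and caffeine concentration" and alpha-amylase were measured. The Project summary gives the same schedule: "After the simulation match, saliva samples were collected from the participants again". Between the two samples come 10 minutes of chewing, a 15-minute warm-up, free self-stimulation, a grip test and two 3-minute rounds.

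The match is partly prescribed and partly maximal. After the paced falls that open each minute, "The participants then try to complete the maximum number of falls in 20 seconds". The last block of a round is longer: "During the 3rd minute, the duration of continuous wrestling was extended to 30 seconds".

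Under Statistical analysis, alpha-amylase is tested by a two-way repeated-measures ANOVA (trial by time). Work done does not enter that analysis.

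**The concern.** The marker of the proposed mechanism is measured only after the performance it might explain, and after an amount of work that is itself the primary outcome. If the gum increases falls, the CAF sample follows more maximal work than the PL sample. The protocol itself accepts that physical action raises sympathetic activity: it says the self-stimulation before the match is meant to do so. Extra falls could therefore raise alpha-amylase without any other action of caffeine.

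At stake is the meaning of a significant trial-by-time interaction. Three accounts fit it equally well: caffeine raised sympathetic activity and so produced more falls; caffeine produced more falls, and these raised sympathetic activity; or both. The Introduction's rationale needs the first. This is not a matter left to an analysis plan. Sampling times are fixed by the protocol, and no analysis of these two samples recovers the missing contrast between gum and match.

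**Working it through.** **1. Order of events** (Methods, Protocol subsection)

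| Step | Duration | Saliva |
|---|---|---|
| Arrival | – | sample 1 |
| Gum | 10 min | none |
| Warm-up | 15 min | none |
| Self-stimulation, grip test | not stated | none |
| Round 1, break, round 2 | 3 + 0.5 + 3 = 6.5 min | none |
| After the match | – | sample 2 |

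Sample 2 comes at least 10 + 15 + 6.5 = 31.5 minutes after chewing starts. The protocol expects peak blood caffeine 15 minutes after the gum is spat out, which is the end of the warm-up. No saliva is taken then.

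**2. How much of the match can differ between trials.** The maximal blocks last 20 + 20 + 30 = 70 s per round, or 2 × 70 = 140 s in all. That is 70/180 = 39% of each round. The rest is paced falls or rest. Work can differ only in the maximal blocks, and those blocks generate any CAF-PL difference in falls.

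**3. What the test estimates.** With two trials and two times, the trial-by-time interaction is equivalent to a paired t-test on

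A = (post − pre) in CAF − (post − pre) in PL.

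Randomised order makes the mean of A a total effect of the gum: any direct part plus any part through work. The two parts cannot be separated from A.

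**4. Illustration of the work path alone.** The documents give no figure linking falls to alpha-amylase, so there is no plan figure to reproduce. Let F be a participant's CAF-PL difference in falls, and suppose the gum acts on alpha-amylase only through falls:

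A = b·F + e, with e of mean zero and independent of F.

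Then mean(A) = b·mean(F) and SD(A) = b·SD(F)/r, where r is the correlation of A with F. Hence

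mean(A)/SD(A) = r × d_F, with d_F = mean(F)/SD(F).

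Inputs: n = 16 (Participants section); two-sided 0.05 (the level is the protocol's, two-sidedness is assumed); d_F = 0.8 and r = 0.3 to 0.6 (assumed). The noncentrality is r·d_F·√16, with 15 degrees of freedom.

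| r | r × d_F | noncentrality | chance of a significant interaction |
|---|---|---|---|
| 0.3 | 0.24 | 0.96 | 14.7% |
| 0.6 | 0.48 | 1.92 | 43.5% |

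**5. A second model.** Suppose instead that the pre-to-post rise is proportional to work and set it to 100 units, with an SD of A between 30 and 10 units (all assumed). By simulation with n = 16, the interaction is significant in about 5% of trials with no extra work, in 10% to 47% with 5% extra work, and in 24% to 96% with 10% extra work.

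These percentages are chances of detecting a real indirect effect of the gum. They are not false-positive rates for the total effect. They show only that a significant interaction need not involve any action of caffeine apart from extra work.

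**The case against.** The strongest reply is that randomisation makes any CAF-PL difference causal. This is right, and it limits the point. A reader might infer from the sampling scheme that the trial cannot show any effect of the gum on sympathetic activity. The documents do not support that. The stated purpose concerns sympathetic activity in a simulated match, and both it and the title fit a total effect measured after one. What is lost is narrower: independence from work, and the order in time.

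Second, the Introduction is tentative about the mechanism, the evidence it cites concerns activation during exercise, and no mediation objective is stated. This also stands. The point is therefore a limit on the conclusion, not an error in the planned test.

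Third, the match is not wholly self-paced. That is true, but the maximal blocks produce the difference in falls, so the argument holds.

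Fourth, a reader might apply the protocol's sample-size effect of 2 to the falls and obtain much larger percentages. That figure comes from completion time on another wrestling test after a high caffeine dose. It does not describe falls here and is not used.

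Finally, a reader might look to heart rate in the warm-up for the missing pre-match contrast, since "After the participants putted on heart rate monitor" precedes the gum step. The documents do not say that warm-up readings were stored. They fix the warm-up's length but not its intensity, and a newly named indicator would now be post hoc. It should not decide how the alpha-amylase result is read.

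**Conclusion.** The point holds as a limit on interpretation. As designed, the alpha-amylase comparison can show a total effect of the gum on the post-match response. It cannot show that the gum raised sympathetic activity independently of the work done, or that activation came first and explains the falls. This follows from the sampling times and the definition of the primary outcome, with no numerical assumption.

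The size of the work path is unknown. The illustrative 15% to 44% rests on an assumed falls effect and assumed correlations, and the wider ranges of the second model on an assumed proportional rise and assumed SDs. Neither estimates what happened in this trial. The comparison of falls is unaffected.

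**What to change.** 1. Define the secondary outcome as the post-match alpha-amylase response, and state that the CAF-PL comparison estimates the total effect of the gum, including any effect through work done.
2. Plot each participant's CAF-PL difference in alpha-amylase change against his CAF-PL difference in falls, as descriptive support only. Falls are measured after the gum and may be affected by it, so an estimate adjusted for falls would not be a causal direct effect.
3. State that no work-independent or mediating sympathetic effect will be concluded from this outcome, and bring the Introduction's mechanism into line with that.

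A saliva sample at the end of the warm-up, before self-stimulation, would have separated an effect before the match from one through match work. The Study design section says the study concluded on 23 December 2024, so this applies only to a future trial.

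The cost is a few sentences and one plot from data the protocol already collects. The price is a weaker mechanistic claim.
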